8.4 DATA SOURCES

The study is a survey using primary data collection conducted through a HCP questionnaire and collected by web or phone. Both methods will be proposed to HCPs and they will be given the choice to select one or the other.

8.4.1 Identification of HCPs

In each country, HCPs will be identified according to their speciality as specified in using the proprietary **Exercise** lists, which is representative of the relevant HCP population and has a coverage of above 90%.

is a comprehensive worldwide database of healthcare professionals. It is constructed according to ISO 9001: 2015 Quality Management Systems Requirements. The lists are representative of the HCP population in the selected countries. In any case, all HCPs in the study countries who are potential prescribers (i.e., oncologists or pulmonologists) of Alecensa will be considered as the target population and will be randomly enrolled, on an ongoing basis keeping a representative regional spread until the study size is reached or the list is exhausted (see 8.4.2 Data Collection) (Kish 1995).

8.4.2 Data Collection

Questionnaire

The questionnaire will include multiple-choice, open, and closed questions as appropriate and will be sent to the participating HCPs to collect information on their awareness, knowledge, and clinical practice about the specific guidance included in the label to minimize the risk of ILD/pneumonitis, hepatotoxicity, photosensitivity, bradycardia, severe myalgia, and CPK elevations.

The questionnaire will be translated into the relevant local languages. Translation will be done using the back and forth method of translation (i.e., from English into local language and then from local language into English). Physicians selected randomly from a panel of active physicians (i.e., physicians who regularly complete questionnaires of this nature) of the relevant specialities in the **second** database will ensure the meaning of the questions is retained in the translations (2-3 physicians per country). Before deployment, the questionnaire will be field tested to ensure accuracy.

The HCP questionnaire completion is estimated to take about 15 minutes.

Conduct of survey

For data collection a period of up to 6 months is planned. Data collection will be conducted between 18 and 24 months after the first line treatment approval by the European Medicines Agency (EMEA). In this 6-month time frame the fieldwork start date may vary by country based on the date of local market launch.

To ensure comprehension of the invitation and the survey, the entire HCP outreach will be conducted in the respective country's local language. The survey and invitation as well as any reminders will be translated by native speakers of the respective language at

HCPs will be randomly contacted by emails or phone calls, when needed, according to their strata (country and if applicable speciality) by the team. Their recruitment will be done as follows:

- HCPs will be invited to participate in the survey (via emails or phone calls). The survey background and objectives, the contact information for questions, and the proposed compensation will be explained to the HCPs at this step. will ensure that the compensation is in line with relevant guidelines of each country and that it only constitutes a compensation for the actual effort and time that is needed to fill-in the questionnaire
- If they agree to participate in the survey, they will click on the link included in the email to access the survey and the instructions for the web questionnaire completion
- HCPs can also choose to participate in the survey by phone in the local language. In this case, an appointment for a phone interview will be scheduled with them

- HCPs who self-report having treated patients with Alecensa at least once in the 6 months prior to the study and are not employed by a pharmaceutical company,
 , or by regulatory bodies will be eligible to complete the survey. Both parameters are included as screening questions in the questionnaire
- Once HCPs have passed the screening questions of the questionnaire, they are moved through the questions one question at a time. HCPs can only progress to the next question when the previous question was answered. Only wholly completed questionnaires can be submitted
- If the questionnaire is not completed within one week, the HCPs will be sent a reminder by email one week after the link was sent to them
- If the study sample size is not achieved in the stratum (speciality/country), a second reminder by phone will be conducted 1.5 weeks after the link has been sent
- If the questionnaire is still not fully completed, a third and final reminder will be sent to the HCPs by email approximately three weeks after the start of the survey

If necessary, i.e., if the minimum number of needed responders is still not reached, the recruitment will be continued to achieve the study sample size-in a specific stratum.

A HCP will be considered as unreachable if he/she has been contacted between 3 and 5 times without any answer being received.

For each HCP of the sample, the number of contacts, and the date and time when he/she completed the web questionnaire will be recorded. The recruitments in each stratum (HCP speciality/country) will be stopped when the target is reached. If the files have been exhausted in any particular stratum, the recruitments in this stratum will be prematurely ended and a strategy will be determined to adjust the sample size with associated weighting.

The number of HCPs passing the screening questions, incidence rate, and the survey response rate will be monitored regularly by **series**. If the survey response rate or incidence rate is too low, the recruitment may be undertaken in additional countries.

8.4.3 Data Collected at Study Completion

Not applicable

8.4.4 Safety Data Collection

Not applicable

8.5 STUDY SIZE

8.5.1 Study size calculation

The sample size formula based on the normal approximation to the binomial is the following:

$$n = \frac{P \cdot (1-P) \cdot \left(Z_{1-\alpha/2}\right)^2}{e^2},$$

Where P is the expected proportion, e is one half the desired width of the confidence interval, and $Z1-\alpha/2$ is the standard normal Z value corresponding to a cumulative probability of $1 - \alpha/2$ (e.g., if $\alpha = .05$ then Z = 1.96).

The proportions of interest (p) here are the proportions mentioned under specific objectives above. As p is not known in advance, we consider it to be 50% (maximum uncertainty). Such a hypothesis yields the most conservative i.e., the largest sample size. For example, the required sample size would be 100 for precision levels of 10%. Table 2 below provides precision of the estimate (width of 95% CI around the estimate) for a range of sample sizes.

Sample Size	Statistical Precision (%)
100	±9.8
150	±8.0
200	±6.9
250	±6.2
300	±5.7
350	±5.2
400	±4.9

For this survey, a sample size of approximately 200 completed questionnaires aggregated across the target countries is being considered, which is based on both statistical and practical considerations. With a sample size of 200, the statistical precision around the estimate will be $\pm 6.9\%$; the precision will increase with larger sample sizes. It is to be noted that the final survey sample size will depend on HCPs' willingness to participate in the survey. While the target is 200 respondents, all completed responses received by the cut-off date will be included in the analysis.

Assuming that the survey response could be as low as 10%, about 2,000 HCPs will be invited to participate in this survey in order to increase the number of HCPs passing the screening questions and the likelihood that at least 200 HCPs fill out the questionnaire This estimate is in line with the low response rate reported for similar surveys in the literature (Agyemang et al. 2017).

Ideally, the sample of 200 HCPs should be proportionally split between the selected countries based on the number of HCPs in each country and then further split among HCP specialties based on their real proportion. However, due to large variance in the number of HCPs in targeted countries such a distribution would yield to a number of interviews in smaller countries (such as Sweden) or/and in specialties too small to allow the applicability of common statistical methods. A pragmatic split will therefore be implemented to allocate a sufficient sub-sample size to the less represented countries. An example of potential split among countries is given in Table 3.

We will then weight back the results according to the real proportion of HCPs from lists to avoid the skewness of the overall sample.

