8.5.2 Sampling Plan

For each selected country, the sample survey will include HCPs identified and recruited from the **selected** list. The **selected** database covers above 90% of the specialities of

interest (i.e., oncologists and pulmonologists) in the target countries (i.e., Austria, Belgium, Germany, Spain, Sweden, and the UK).

A screening question will check whether the physician did ever treat patients with Alecensa in the last 6 months prior to the survey and can therefore be considered for the survey.

With respect to the indication for Alecensa the survey will be deployed amongst oncologists and pulmonologists. The split between the two will depend on who provides care for NSCLC patients in each respective country.

As per sample size defined above and the number of selected countries, the following potential split of sample into strata of the HCPs by country is planned thereby taking into account the size of the country and the HCP universe size (see Table 3)

This table is indicative and will be adjusted according to the final list of countries included and the responsive HCP per strata. It is aimed to have at least 20 completed questionnaires per country.

Planned Country	Overall Number of Completed Questionnairesª	Universe Oncologists ^ь	Universe Pulmonologists ^ь
Germany	50	2900	2400
United Kingdom	45	2700	2500
Spain	45	2300	N/A¢
Austria	20	300	600
Belgium	20	500	700
Sweden	20	600	300
Total	200	N/A	N/A

Table 3 Split of Sample by Country According to a Sample of 200 HCP Questionnaires

^aThe split between specialties depends on the involvement of specialties in the management of advanced lung cancer patients in the different target countries and may be subject to change.

^bUniverse: Numbers of oncologists/pulmonologists in the country according to **according to according (version June** 2018)

^cOnly oncologists are relevant in the treatment of NSCLC in Spain

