8.5.3 Sample adjustment

Since the relative weight of each country and each category of HCPs in the final sample may be different from its real proportion, the extrapolation of the raw survey results to the overall target population would not be relevant without adjustment. The survey results will be weighted to reflect the real proportion of the countries and the real proportion of each speciality in order to allow the extension of the survey results to the

Alecensa—F. Hoffmann-La Roche Ltd Protocol BO40643, Version 1 overall target population. Both unweighted and weighted results will be presented in the report.

A weight variable will be applied to each statistical unit (i.e., the HCPs) during the results calculation to correct any over-or under-sampling that may have occurred for a country or speciality. This weight variable will indicate how many unit(s) of the population of interest an observation will count in a statistical procedure. Its value will change per country and per speciality. The weights will be normalized to obtain their sum equal to the sample size.

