8.7 DATA ANALYSIS

General considerations

The statistical analysis will be conducted using the SAS software (Version 9.4 or above).

The statistical results of the HCP data will be presented in the same report, by country, by speciality, and in total (see Table 4 as example).

Continuous variables will be presented by their number (of valid cases), mean, standard deviation, and median, Q1, Q3, minimum, and maximum.

Categorical variables will be presented as the total number and relative percentage per category. These will be the percentage per category.

In case of multiple choice questions, the frequency of each option provided by the physicians will be reported in the statistical results. Different combinations of the answers provided will not be considered.

Confidence intervals of 95% will be estimated, as appropriate.

Country	Speciality (Pulmo)	Speciality (Onco)	All (unweighted)	All (weighted)
Country 1	(N=xx)	(N=xx)	(N=xx)	(N=xxx)
answer 1	xx (xx.x%)	xx (xx.x%)	xx (xx.x%)	xx (xx.x%)
answer 2	xx (xx.x%)	xx (xx.x%)	xx (xx.x%)	xx (xx.x%)
answer 3	xx (xx.x%)	xx (xx.x%)	xx (xx.x%)	xx (xx.x%)
Country 2	(N=xx)	(N=xx)	(N=xx)	(N=xx)
answer 1	xx (xx.x%)	xx (xx.x%)	xx (xx.x%)	xx (xx.x%)
answer 2	xx (xx.x%)	xx (xx.x%)	xx (xx.x%)	xx (xx.x%)
answer 3	xx (xx.x%)	xx (xx.x%)	xx (xx.x%)	xx (xx.x%)
Country 3	(N=xx)	(N=xx)	(N=xx)	(N=xx)
answer 1	xx (xx.x%)	xx (xx.x%)	xx (xx.x%)	xx (xx.x%)
answer 2	xx (xx.x%)	xx (xx.x%)	xx (xx.x%)	xx (xx.x%)
answer 3	xx (xx.x%)	xx (xx.x%)	xx (xx.x%)	xx (xx.x%)
Country x	(N=xx)	(N=xx)	(N=xx)	(N=xx)
answer 1	xx (xx.x%)	xx (xx.x%)	xx (xx.x%)	xx (xx.x%)
answer 2	xx (xx.x%)	xx (xx.x%)	xx (xx.x%)	xx (xx.x%)
answer 3	xx (xx.x%)	xx (xx.x%)	xx (xx.x%)	xx (xx.x%)

Table 4 Mock Tables to Implement in the Statistical and Study Reports

Alecensa—F. Hoffmann-La Roche Ltd

Protocol BO40643, Version 1

Overall - unweighted results	(N=xx)	(N=xx)	(N=xx)	(N=xxx)
answer 1	xx (xx.x%)	xx (xx.x%)	xx (xx.x%)	xx (xx.x%)
answer 2	xx (xx.x%)	xx (xx.x%)	xx (xx.x%)	xx (xx.x%)
answer 3	xx (xx.x%)	xx (xx.x%)	xx (xx.x%)	xx (xx.x%)
Overall - weighted results	(N=xx)	(N=xx)	(N=xx)	(N=xxx)
answer 1	xx (xx.x%)	xx (xx.x%)	xx (xx.x%)	xx (xx.x%)
answer 2	xx (xx.x%)	xx (xx.x%)	xx (xx.x%)	xx (xx.x%)

Note: the table structure may be adjusted for the final study report.

Handling of missing data

. . . .

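### The ±6.9% precision in Protocol 8.5.1 holds only for the unweighted result; under Table 3 the weighted result that the plan generalises has about ±7.4%.

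*Protocol*

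**What the plan says.** Section 8.5.1 derives the study size from one formula: "The sample size formula based on the normal approximation to the binomial is the following". The proportion is set at its worst case, "As p is not known in advance, we consider it to be 50% (maximum uncertainty"), and "a sample size of approximately 200 completed questionnaires aggregated across the target countries is being considered". The resulting statement is "With a sample size of 200, the statistical precision around the estimate will be" ±6.9%. Neither the text nor Table 2 limits that figure to the unweighted result.

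The same section then gives up proportional allocation: "A pragmatic split will therefore be implemented to allocate a sufficient sub-sample size to the less represented countries", with results weighted back to the list proportions afterwards. Table 3 (8.5.2) shows the intended allocation and the number of oncologists and pulmonologists on the lists in each country. It is described there as indicative.

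Section 8.5.3 makes the weight vary by country and by speciality and adds: "The weights will be normalized to obtain their sum equal to the sample size". Section 8.9 says the raw results cannot be carried over to the target population unless the adjustment is made. Weighted and unweighted results are both to be reported. On intervals, section 8.7 says only: "Confidence intervals of 95% will be estimated, as appropriate".

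**The concern.** The only precision figure in the plan belongs to one estimate, and the generalisation rests on another. ±6.9% assumes 200 equally weighted respondents. The weighted estimate uses the same 200 respondents with unequal weights, which raises its variance. Normalising the weights to sum to 200 rescales them but leaves their spread, and so the inflation, unchanged.

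The survey tests no hypothesis (the ENCePP checklist marks item 2.1.4 as not applicable), so expected precision is the whole statistical part of the case for 200 completes. At stake is a stated precision that is somewhat too favourable for the result that will be generalised. There is also a conditional risk: if intervals for weighted results were computed as though the weight total of 200 were 200 equally weighted observations, they would be too narrow.

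**Working it through.** **Inputs.** n = 200, P = 0.50 and Z = 1.96 from 8.5.1; completes and list sizes from Table 3. Pulmonologists in Spain are not counted, following the table's own footnote.

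**1. The plan's figure.** e = Z·√(P(1−P)/n) = 1.96·√(0.25/200) = 6.93%. For n = 100, 150, 200, 250, 300, 350 and 400 the formula gives 9.80, 8.00, 6.93, 6.20, 5.66, 5.24 and 4.90, so all of Table 2 reproduces. The arithmetic is correct for equal weights.

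**2. Weighted estimate with country weights.** Let W be a country's share of the total list and a its share of the completes. With a common P, the variance is P(1−P)·ΣW²/n_h, so the design effect is deff = ΣW²/a.

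| Country | List total | W | Completes | a | Relative weight W/a | W²/a |
|---|---|---|---|---|---|---|
| Germany | 2900 + 2400 = 5300 | 0.335 | 50 | 0.250 | 1.34 | 0.450 |
| United Kingdom | 2700 + 2500 = 5200 | 0.329 | 45 | 0.225 | 1.46 | 0.481 |
| Spain | 2300 | 0.146 | 45 | 0.225 | 0.65 | 0.094 |
| Austria | 300 + 600 = 900 | 0.057 | 20 | 0.100 | 0.57 | 0.032 |
| Belgium | 500 + 700 = 1200 | 0.076 | 20 | 0.100 | 0.76 | 0.058 |
| Sweden | 600 + 300 = 900 | 0.057 | 20 | 0.100 | 0.57 | 0.032 |
| Total | 15,800 | 1 | 200 | 1 | | 1.148 |

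- Effective n = 200/1.148 = 174.
- Half-width = 1.96·√(0.25·1.148/200) = 7.43% (7.38% with a finite population correction).
- Completes needed in the same allocation to bring the weighted half-width back to 6.93%: 200·1.148 = about 230.

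**3. Which specialities are counted.** Table 3 leaves this open by country. I took oncologists, pulmonologists or both in each country (Spain oncologists only), with completes split in proportion within the country. Over all combinations the half-width runs from 6.96% to 8.24%. Oncologists only everywhere gives deff 1.116 and 7.32%. Oncologists only in Germany, the United Kingdom and Spain, with both specialities elsewhere, gives deff 1.011 and 6.97%. No combination falls below the equal-weight 6.93%.

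**4. Non-proportional speciality split (assumed).** The plan gives no split of completes between specialities. With country-by-speciality weights, deff = n·ΣW²/n_h over those cells. Applying the same split in every country except Spain:

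| Oncologist:pulmonologist completes | deff | Effective n | Half-width |
|---|---|---|---|
| In proportion to lists | 1.148 | 174 | 7.43% |
| 50:50 | 1.162 | 172 | 7.47% |
| 60:40 | 1.185 | 169 | 7.54% |
| 70:30 | 1.316 | 152 | 7.95% |
| 80:20 | 1.666 | 120 | 8.94% |

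**5. Other values of P.** The ratio √1.148 = 1.07 applies at every P. At P = 0.60 the half-width goes from 6.79% to 7.28%; at P = 0.75, from 6.00% to 6.43%.

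**6. Normalised weights.** Taking the weight total of 200 as n returns 6.93% at P = 50%, whatever the weights. If intervals were built that way, the multiplier in true standard errors would be 1.96/√deff: 1.83 at deff 1.148 (coverage about 93%) and 1.52 at deff 1.666 (about 87%).

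**The case against.** The best defence is that ±6.9% is a planning figure at a declared worst case. At P = 0.75, the target for two of the three success criteria, the weighted half-width is 6.43%, inside the stated figure; with deff 1.148 this holds once P is about 0.68 or more. Table 3 is openly indicative, the sample size also rests on practical considerations, all completed responses are analysed, and no success criterion uses a confidence limit. The unweighted result, for which ±6.9% is right, is reported as well.

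Much of that stands, and it keeps the point small. It does not rescue the figure. The plan chose P = 50% as its basis, and on that basis the weighted estimate is less precise than stated. At any other P the matching equal-weight figure is also missed, by the same factor. Disproportionate allocation is the stated intent, not an accident of the example table.

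Three stronger readings are tempting but not supported:

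- A reader might infer that ±7.4% is the best the design can deliver. It is not: speciality mixes that Table 3 leaves open come down to about ±7.0%.
- A reader might infer much larger inflation by weighting to the sales shares in Table 1. The plan weights to physician lists; Table 1 supports the choice of countries only.
- A reader might infer that the weighted intervals will ignore the design. The protocol does not say so. Normalised weights are compatible with a correct variance, and the choice of software procedure can be left to the statistical analysis plan.

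**Conclusion.** The point holds as a matter of scope. ±6.9% is computed correctly but stated without qualification, and it describes the unweighted result while the plan generalises from the weighted one. Under Table 3, with both specialities counted as listed, country weights and P = 50%, the loss is about half a percentage point (6.93% to 7.43%), equivalent to 26 of 200 respondents. It could be almost nil or appreciably larger: about ±7.0% to ±8.2% by the specialities counted, and ±7.5% to ±8.9% under the assumed 50:50 to 80:20 splits.

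These figures assume the same P in every stratum; real differences between countries would lower the stratified variance slightly. No decision rule changes, and the result does not call for more respondents. It is worth correcting because the statement is wrong as written for the estimate that matters and the correction is cheap.

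**What to change.** In section 8.5.1 and under Table 2, label ±6.9% as the precision of the unweighted result. Beside it give the expected precision of the weighted result: about ±7.4% under Table 3 at P = 50% (design effect about 1.15, effective n about 174), with the range and the speciality assumption behind it. Recompute when the countries and speciality split are final.

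In 8.5.3 or 8.7, add that 95% confidence intervals for weighted results will use a variance that reflects the weights and strata, because normalising the weights to sum to 200 does not remove the inflation.

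The cost is a few sentences and a slightly less favourable stated figure. The sample size and recruitment stay as they are.

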8.5.2 Sampling Plan

For each selected country, the sample survey will include HCPs identified and recruited from the **selected** list. The **selected** database covers above 90% of the specialities of

interest (i.e., oncologists and pulmonologists) in the target countries (i.e., Austria, Belgium, Germany, Spain, Sweden, and the UK).

A screening question will check whether the physician did ever treat patients with Alecensa in the last 6 months prior to the survey and can therefore be considered for the survey.

With respect to the indication for Alecensa the survey will be deployed amongst oncologists and pulmonologists. The split between the two will depend on who provides care for NSCLC patients in each respective country.

As per sample size defined above and the number of selected countries, the following potential split of sample into strata of the HCPs by country is planned thereby taking into account the size of the country and the HCP universe size (see Table 3)

This table is indicative and will be adjusted according to the final list of countries included and the responsive HCP per strata. It is aimed to have at least 20 completed questionnaires per country.

Planned Country	Overall Number of Completed Questionnairesª	Universe Oncologists ^ь	Universe Pulmonologists ^ь
Germany	50	2900	2400
United Kingdom	45	2700	2500
Spain	45	2300	N/A¢
Austria	20	300	600
Belgium	20	500	700
Sweden	20	600	300
Total	200	N/A	N/A

Table 3 Split of Sample by Country According to a Sample of 200 HCP Questionnaires

^aThe split between specialties depends on the involvement of specialties in the management of advanced lung cancer patients in the different target countries and may be subject to change.

^bUniverse: Numbers of oncologists/pulmonologists in the country according to **according to according (version June** 2018)

^cOnly oncologists are relevant in the treatment of NSCLC in Spain

